7.0 OUTCOMES

7.1 PRIMARY OUTCOME MEASURES

Treatment equivalence as evaluated by: Disease-free survival at 4.5 years post-surgery, as measured by the time interval between date of surgery and date of first recurrence. Histological confirmation of recurrent disease will prove the presence of recurrent disease.

7.2 SECONDARY OUTCOME MEASURES

Patterns of recurrence: date and localization of 1st recurrence as confirmed histologically –
 pelvic versus distal.

- Treatment related morbidity, as evaluated by:
 - Intraoperative complications injury to bladder, ureter, bowel; vascular injury and bleeding, nerve injury;
 - Perioperative (time to discharge from hospital): urinary tract infection, urinary retention, ileus, cardiac (myocardial infarction, atrial fibrillation), pulmonary (edema, atelectasis, pneumonia), renal and cerebrovascular morbidity. Wound and vault complications (infection, breakdown, and dehiscence). Septicaemia and thromboembolic complications (DVT, PE). Lymphocyst or abscess formation;
 - Early postoperative (< 4 weeks): Wound and vault complications (infection, dehiscence). Lymphocyst, Abscess formation, Lymphoedema or Fistula formation;
 - Long-term morbidity (4 weeks to 6 months): Lymphoedema, incisional hernia formation, vaginal eviseration.
 - Estimated blood loss: As defined by the total volume of suctioned fluids minus the volumes of irrigation fluids used at the completion of surgery. In addition, blood loss will be reviewed in hemoglobin change from baseline. A Full Blood Count (hemoglobin) will be taken before and the morning after the operation;
 - Postoperative pain and analgesic consumption using pain scores and analgesic consumption measurements;
- Costs: measured as the incremental cost per unit of improvement in functional outcome, measured in terms of the primary outcome plus using quality-adjusted life years (QALYs) to undertake a cost-utility analysis;
- Quality of life: Change in Quality of Life using Functional Assessment of Cancer Therapy Cervical (FACT-Cx), the MD Anderson Symptom Inventory (MDASI, Short Form-12 (SF-12) and EuroQoL-5D (EQ-5D) between Baseline (pre-surgery) and 6 months after surgery.
- Pelvic Floor Distress Inventory: measures symptom severity and quality of life changes in women with pelvic floor disorders. The Pelvic Floor Distress Inventory (PFDI) provides a standardized, reproducible assessment of the patient's symptoms and their effect on daily life⁸⁸.
- Overall survival at 4.5 years follow-up
- Feasibility of sentinel lymph node biopsy in this group of patients.

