3.2 RATIONALE FOR THE QUALITY OF LIFE

Retrospective studies suggest equivalency between the laparoscopic and open approaches to radical hysterectomy in regards to surgical specimens obtained ⁷⁹ and likely disease-free and overall survivals ⁸⁰ ⁸¹ ⁸² ⁸³ ⁸⁴ ⁸⁵ ⁸⁶. Thus, quality of life could be seen as one of the most significant factors in recommending one approach over the other and therefore an extremely important endpoint for this protocol. In the GOG LAP-2 protocol⁸⁷, a trial evaluating a comparison between hysterectomy by laparotomy or laparoscopy, the investigators found equivalency adequacy of the two surgical approaches however a significant difference in short term quality of life favoring laparoscopy. As expected, patients who underwent laparoscopy had a faster return to baseline functioning compared with those patients who had undergone laparotomy which translated into improved short-term quality of life. By 6 months, however, patients in both cohorts were reporting equivalent quality of life parameters. Quality of life surveys employed with this Phase III clinical trial will encompass important endpoints such as postoperative pain and related symptoms using the MD Anderson Symptom Assessment Index (MDSAI), as well as cancer specific Functional Assessment of Cancer Therapy (FACT-Cx) and the general 12-Item Short-Form Health Survey (SF-12).

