10.2 ANALYSIS OF STAGE II (PHASE III STUDY)

Disease-free survival and overall survival curves will be estimated using the Kaplan-Meier method. The primary comparison of survival distributions will be with the logrank test. Secondary analyses will adjust for prognostic factors using appropriate regression models (e.g. Cox proportional hazards model). All measures of efficacy will be compared by an intention-to-treat analysis including all randomized patients. Toxicity will be analyzed by treatment received. Ninety-five percent confidence intervals will be reported for the differences between the treatment arms.

Descriptive statistics for treatment-related adverse events as well as Quality of life (FACT-Cx, SF-12, MDASI, EQ-5D) and subscales (physical well-being, social well-being, emotional well-being, functional well-being, cervical cancer specific well-being and body image scale), will be calculated for each randomization group at each assessment.

Similarly, descriptive statistics will also be calculated for other outcomes, such as pain scores, anxiety and depression scores and analgesic consumption, etc.

Continuous variables will be assessed for normality and equality of variances between groups. Discrete variables (eg. presence/absence of post-operative infection) will be summarized by frequencies/proportions.

For continuous variables, analysis of variance and/or regression will be used, where appropriate. If assumptions for these tests are violated, alternative non-parametric tests will be used. Difference between groups with respect to discrete variables will be evaluated by using chi-squared tests.

Exploratory analyses adjusting for prognostic factors including age, tumor size, stage, grade of differentiation, depth of myometrial invasion, lymph node involvement, type of treatment, and ECOG status will be performed using proportional hazards regression methods. The impact of baseline QoL on survival will also be investigated.

Provided sufficient patient numbers, outcomes in regards to treatment costs will be analyzed country-specific by the individual investigator of that country.

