11.1 ECONOMIC ANALYSIS

We will assess the cost-effectiveness of the intervention (TLRH \pm Laparoscopic Pelvic/Aortic Lymph Node Dissection) relative to standard treatment alone (TARH \pm Pelvic/Aortic Lymph Node Dissection), calculated as the incremental cost per unit of improvement in functional outcome, and measured in terms of the primary outcome.

The outcomes of this part of the economic analysis will be in terms of costs per disease and treatment specific difference in quality of life at six months. More specifically, costs per fewer days' treatment-related morbidity, shorter hospital stays, less days with post-operative pain, and less analgesic consumption. By assessing the difference in cost between the standard treatment and the proposed intervention, it can be ascertained which of the two treatments represents the most sound investment in terms of the improvement in quality of life.

We will also measure the quality-adjusted life years (QALYs) gained with the intervention and use this to undertake a cost-utility analysis. The QALY calculations will be based on health status measures for trial participants, with valuations of changes in health status and quality of life based on the EQ-5D. Several viewpoints will be considered for the economic analyses, including those of health system purchasers, households and society in general.

This part of the economic analysis allows us to express outcomes in costs per QALY. The aim of this generic outcome measure is to assess whether the study intervention represents value for money as compared to alternative interventions (including for other conditions), and as compared to the various threshold values below which an intervention is considered good value for money (in Australia \$40,000 per QALY is often used).

In terms of measuring costs, a number of components will be considered, including: the intervention costs; the provision of information booklets to patients; GP and specialist consultations; radiology and imaging; prescriptions, over-the-counter medications; community health and social services; days off work; and informal care by family and friends. Direct costs will be obtained for samples of patients, stratified by hospital, operation and outcome, using a bottom-up approach by recording the volume of resource use in both arms of the trial, and then applying a unit cost to each component. Data on all patients' use of healthcare services will be collected using a combination of retrospective

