12.3 POST-OPERATIVE (VISITS 3 -VISIT 6)

The following procedures will be performed at visits scheduled at 1 week, 6 weeks, 3 months, and 6 months post surgery:

Day 1 – after surgery:

- Record post operative Hemoglobin level to Surgery eCRF if done (Day 1 after surgery)
- Record laboratory results (if clinically indicated)

Visit 3 – Post Op Visit 1 = Week 1 (must be collected within 3 days either side of due date and may be obtained via medical visit, telephone contact or postal correspondence):

- Provide patient with Quality of Life instruments (FACT-Cx, SF-12, EQ-5D, MDASI);
- Provide patient with Health Services Questionnaire;
- Review ECOG performance score;
- Weight if available
- Assess patients for their individual pain level using linear analogue scale
- Record Full blood count and ELFT's if available
- Physical examination not a requirement at this time point, however record done/not done
- Adverse events assessment (CTCAE v3.0);
- Update concomitant medications
- Update concomitant illnesses

Visit 4 – Post Op Visit 2 = Week 6 (must be collected within 1 week either side of due date and may be obtained via medical visit, telephone contact or postal correspondence)

Visit 5 – Post Op Visit 3 = Month 3 (must be collected within 2 weeks either side of due date and may be obtained via medical visit, telephone contact or postal correspondence)

Visit 6 – Post Op Visit 4 = Month 6 (must be collected within 1 month either side of due date and may be obtained via medical visit, telephone contact or postal correspondence)

Version 4 October 2014

The following procedures will be performed at Visit 3-5 (aka Post Op Visits 1-4)

- Provide patient with Quality of Life instruments (FACT-Cx, SF-12, EQ-5D, MDASI)
- Provide patient with Pelvic Floor Distress Inventory (every 6 months postoperatively)
- Provide patient with Health Services Questionnaire;
- Review ECOG performance score;
- Assess patients for their individual pain level using linear analogue scale
- Record Weight (kg);
- Adverse events assessment (CTCAE v3.0);
- Update concomitant medications
- Update concomitant illnesses
- Record laboratory results (if clinically indicated)

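### The quality-of-life outcome is fixed at 6 months, when the trial cited as its rationale found the arms equal, and no early contrast is named although early scores are collected.

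*Protocol*

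**What the plan says.** Protocol section 3.2 calls QoL "an extremely important endpoint for this protocol". It cites a trial of hysterectomy by laparotomy or laparoscopy that reported "a significant difference in short term quality of life favoring laparoscopy", and then adds: "By 6 months, however, patients in both cohorts were reporting equivalent quality of life parameters".

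Section 7.2 defines the QoL outcome as the change in FACT-Cx, MDASI, SF-12 and EQ-5D "between Baseline (pre-surgery) and 6 months after surgery".

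Section 12.3 has post-operative "visits scheduled at 1 week, 6 weeks, 3 months, and 6 months post surgery". Appendix 1 lists all four instruments at baseline and at each of these visits.

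Section 10.2 plans descriptive QoL statistics that "will be calculated for each randomization group at each assessment". For testing it has a general sentence: "For continuous variables, analysis of variance and/or regression will be used, where appropriate". It also promises 95% confidence intervals for differences between arms. It names no visit, repeated-measures model or covariate for QoL.

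Section 11.1 expresses part of the economic result as cost per "treatment specific difference in quality of life at six months". The same section also plans cost ratios for morbidity days, hospital stay, pain days and analgesic use, and a cost-utility analysis with QALYs from EQ-5D.

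**The concern.** The reason given for measuring QoL and the outcome used to measure it point to different times. The cited evidence places the advantage of laparoscopy early and reports that it had gone by 6 months. Section 3.1 is consistent with an early window for this operation, since it puts average recovery after open radical hysterectomy at 5 to 6 weeks. The outcome in 7.2 nevertheless rests on 6 months, and the earlier scores have no named comparison.

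Two things are at stake. The defined QoL outcome could show no difference even if early recovery differs clearly between the arms. And a cost ratio that divides by a 6-month QoL difference is unstable if that difference is close to zero.

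**Working it through.** The protocol gives no QoL effect size, standard deviation, correlation, power or sample size, so there is no stated figure to reproduce. The numbers below are illustrations on stated assumptions.

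**1. Timing.**

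| Item | Section | Time |
|---|---|---|
| Benefit of laparoscopy in the cited trial | 3.2 | short term |
| Equality in the cited trial | 3.2 | by 6 months |
| QoL scores collected after surgery | 12.3, Appendix 1 | 1 week, 6 weeks, 3 months, 6 months |
| QoL outcome defined | 7.2 | baseline to 6 months |
| QoL difference in the cost ratio | 11.1 | 6 months |

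The defined outcome and the cost ratio both rest on the one visit at which the cited trial saw no difference.

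**2. What a 6-month test can find.** Let d be the true difference in standard deviations, n the number per arm, r the baseline-to-outcome correlation and Φ the standard normal distribution function. Then

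power = Φ(d/SE − 1.96) + Φ(−d/SE − 1.96), with SE = √(2v/n),

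where v = 2(1 − r) for a change score and v = 1 − r² with baseline as covariate. At d = 0 this is 2 × Φ(−1.96) = 5%, whatever n, r or the adjustment.

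**3. What an early test could find.** Take n = 370 per arm (section 9.0, sized for disease-free survival) and assume d = 0.2 at an early visit. For r = 0.5:

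- Change score: v = 1, SE = √(2/370) = 0.0735, d/SE = 2.72, power = Φ(0.76) = 78%.
- Baseline as covariate: v = 0.75, SE = √(1.5/370) = 0.0637, d/SE = 3.14, power = Φ(1.18) = 88%.

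| n per arm | assumed d | analysis | r = 0.3 | r = 0.5 | r = 0.7 |
|---|---|---|---|---|---|
| 370 | 0.2 | change score | 63% | 78% | 94% |
| 370 | 0.2 | baseline covariate | 81% | 88% | 97% |
| 50 (stage 1) | 0.5 | change score | 56% | 70% | 90% |
| 50 (stage 1) | 0.5 | baseline covariate | 75% | 82% | 94% |

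Timing decides whether there is anything to find; adjustment only changes how precisely it is estimated.

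**4. The gain from baseline adjustment.** Variance relative to a change score is (1 − r²) / [2(1 − r)] = (1 + r)/2. For r = 0.4 this is 0.70 and for r = 0.7 it is 0.85, so the variance is 30% to 15% lower.

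**5. The cost ratio.** The ratio is (difference in cost) / (difference in QoL at six months). As the denominator approaches zero the ratio grows without bound and its sign becomes arbitrary.

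**6. SF-12 at week 1.** On the form in Appendix 6, items 4 to 12 ask about the past four weeks; items 1 to 3 ask about health in general or limits now. Section 12.3 allows 3 days either side of week 1, that is days 4 to 10. So 28 − 10 = 18 to 28 − 4 = 24 of the 28 recall days fall before surgery. FACT-Cx (past 7 days), MDASI (last 24 hours) and EQ-5D (today) do not share this problem to the same degree.

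**The case against.** The strongest reply is that nothing in the protocol prevents an early comparison. The scores are collected, they are summarised by arm at each assessment, and section 10.2 offers general methods and confidence intervals for continuous variables. That is true, and an early difference would at least be visible descriptively. But no early comparison is designated, and the choice of time point belongs to the outcome definition, which the protocol gives in 7.2.

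The wording of 7.2 could also be read as the whole period from baseline to 6 months. This does not settle the matter: one reading sets the contrast at 6 months, and the other leaves its timing unspecified.

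The 6-month equality comes from a related trial whose reference title concerns uterine cancer staging. Section 2.2.1 describes radical hysterectomy as a far more complex procedure with more complications. The equality is therefore not a prediction for this trial, and whether a difference persists to 6 months is a legitimate question. This stands, and is why month 6 should be kept.

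Several stronger inferences are tempting but not supported:

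- A reader might infer that the QoL comparison ignores baseline. A change score uses it, and the general sentence in 10.2 leaves covariates open; these may properly sit in a statistical analysis plan.
- A reader might infer that lack of adjustment is why an early benefit would be missed. Step 2 shows that it is not.
- A reader might infer that the economic analysis as a whole fails. Only the six-month QoL ratio is exposed; the QALY analysis and the early-recovery cost ratios in 11.1 are not.
- A reader might infer that SF-12 at week 1 is unusable. Three of its twelve items do not have four-week recall.

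**Conclusion.** The point holds as a mismatch of timing. Section 7.2 sets the QoL outcome at the time when the evidence in 3.2 shows equal arms, and no early contrast is named for visits already in the schedule. The defined outcome can therefore miss the difference that motivates it.

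The size depends on the unknown true differences. With no difference at 6 months, the chance of a significant result there is 5% at any sample size. With an assumed early difference of 0.2 standard deviations and 370 per arm, an early contrast would have 63% to 97% power across the assumed correlations of 0.3 to 0.7 and the two analyses. These figures rest on a normal approximation, complete data and assumed d and r.

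Baseline adjustment is a separate precision gain, with variance 15% to 30% below change scores for assumed correlations of 0.7 to 0.4. The point concerns a secondary outcome and leaves the disease-free survival comparison untouched.

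**What to change.** - **Sections 7.2 and 10.2:** state that the QoL comparison covers all post-operative visits from week 1 to month 6 in one repeated-measures model, with baseline score as covariate and arm-by-visit terms. Name an early visit as the contrast of interest and keep month 6 as the later contrast. Whether the early visit is week 1 or week 6 is the sponsor's choice; the documents do not decide it, but it must be stated before analysis.
- **Section 11.1:** replace the 6-month QoL difference alone with the difference over the whole period to 6 months, as area under the curve. Leave the QALY and early-recovery cost analyses as they are.
- **SF-12:** add a note that week-1 scores are to be interpreted with caution, because the four-week items mostly cover pre-operative days.

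No visit or questionnaire changes. The cost is a wording amendment and slightly more analysis work.

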8.0 RANDOMISATION

All eligible patients will be required to provide informed signed consent before being randomized. Prior to randomization, each patient will be screened for eligibility according to the inclusion and exclusion criteria. A web-based computer randomization procedure will be coordinated centrally from Australia.

Randomization will be performed using the method of minimization with an equal allocation between the two treatment groups. Randomizations will be stratified according to treating centre, and disease stage as determined clinically according to the current FIGO guidelines and patient's age (≤ 70 and > 70 years).

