| APPEND | DIX 10: TRANSLATION FORMS FOR SOURCE DATA FOR NON-ENGLISH SPEAKING SITES | .89 |
| DEEEDE | NCFS | 00 |

PROTOCOL SYNOPSIS

| Protocol Title | LACC - Laparoscopic Approach to Cervical Cancer | | |
|-------------------------|-----------------------------------------------------------------------------------------------------------------------------------------------------------------------------------------------------------------------------------------------------------------------------------------------------------------------------------------------------------------------------------------------------------------------------------------------------------------------|--|--|
| Full Protocol Title | A Phase III Randomized Clinical Trial Comparing Laparoscopic or Robotic Radical Hysterectomy versus Abdominal Radical Hysterectomy in Patients with Early Stage Cervical Cancer | | |
| Indication | Cervical Cancer - FIGO Stage 1A, FIGO Stage 1B1 (as determined by the following examinations: Cervical biopsy/cone biopsy, PV/PR examination, EUA, xray) | | |
| Primary Objective | To compare disease-free survival amongst patients who undergo a total laparoscopic or robotic radical hysterectomy (TLRH) versus those who undergo a total abdominal radical hysterectomy (TARH) for early stage cervical cancer. | | |
| Secondary Objectives | Compare patterns of recurrence between arms. Compare treatment-associated morbidity within 6 months from surgery. Compare the cost effectiveness of TLRH or TRRH versus TARH Compare the impact on Quality of Life (QoL) between arms. Assess pelvic floor function Compare overall survival between arms Determine the feasibility of sentinel lymph node biopsy in this group of patients | | |
| Study Design | International Multicenter Randomized 1:1 Phase III Two-Stage Clinical Trial Stratification for Site and FIGO Stage. | | |
| Stage 1 | The first stage will assess feasibility of recruitment and delivery of the intervention and collect quality of life on the first 100 patients | | |
| Stage 2 | Should the trial be extended, the Trial Management Committee will select one of the following options: Option #1: The disease-free survival at 4.5 years of the TLRH group is compared against the control group disease-free survival rate Option #2: The trial is expanded to a larger randomized equivalence clinical trial (additional 640 patients) assessing disease-free survival at 4.5 years from treatment | | |

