9.0 SAMPLE SIZE

The primary objective of this study is to determine whether Total Laparoscopic (TLRH) or Robotic Radical Hysterectomy (TRRH) is equivalent to Total Abdominal Radical Hysterectomy (TARH) with respect to 4.5 year disease free survival. If the disease free survival does not differ by more than 7% then the two procedures will be considered to be equivalent.

The 4.5 year disease free survival rate for patients undergoing TARH is estimated to be 90%. The following table, based on exponential survival times, gives the sample sizes required for levels of differences in disease free survival rates at 4.5 years. These differences will be regarded as being equivalent based on different accrual and follow-up times. The sample sizes assume a power of 80%, 95% confidence and two-tailed comparisons.

Based on these numbers, for a 4.5-year accrual and 4.5-year follow-up, a total of 740 patients (370 per arm) would be sufficient to declare equivalence with an equivalence margin of 7.2% or less at 4.5 years. If accrual is sufficiently rapid (ie less than 4.5 years), consideration will be given to increasing the sample size to reduce the amount of follow-up required but maintain the equivalence margin. This sample size will have 87% power to detect a non-inferiority margin of the same magnitude.

Table for Option 1 Randomised Design

| 4yr Disease Free Survival difference to be regarded as equivalent | | Years | Total Sample Size | |
|-------------------------------------------------------------------|------|---------|-------------------|------|
| TLRH/TRRH | TARH | Accrual | Follow-up | |
| | | 3 | 3 | 1660 |
| | | 3 | 4 | 1380 |
| 85 | 90 | 3 | 5 | 1190 |
| | | 4 | 4 | 1280 |
| | | 4 | 5 | 1114 |
| | 90 | 3 | 3 | 750 |
| | | 3 | 4 | 760 |
| 84 | | 3 | 5 | 654 |
| 04 | | 4.5 | 4.5 | 740 |
| | | 4 | 5 | 614 |
| | | 5 | 4 | 656 |
| | | 3 | 3 | 794 |
| | | 3 | 4 | 660 |
| 85 | 92 | 3 | 5 56 | |
| | | 4 | 4 | 612 |
| | | 4 | 5 | 532 |

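### The synopsis and section 8 list different allocation factors, and the primary logrank uses none of them; if the factors are prognostic, this costs a little power

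*Protocol*

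**What the plan says.** **Allocation.** The synopsis, under Study Design, describes a 1:1 trial with "Stratification for Site and FIGO Stage". Section 8.0 is more specific: "Randomization will be performed using the method of minimization with an equal allocation between the two treatment groups". It then says "Randomizations will be stratified according to treating centre, and disease stage as determined clinically" and adds a third factor, "and patient's age (≤ 70 and > 70 years"). Age does not appear in the synopsis entry.

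**Analysis.** Section 10.2 states: "The primary comparison of survival distributions will be with the logrank test". It names no strata or covariates for that test. Adjustment comes afterwards: "Secondary analyses will adjust for prognostic factors using appropriate regression models (e.g. Cox proportional hazards model"), followed by "Exploratory analyses adjusting for prognostic factors including age, tumor size, stage, grade of differentiation" and further items. Age and stage are in that exploratory list; centre is not named. Section 10.2 also promises 95% confidence intervals for differences between arms, without saying whether they are adjusted.

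**The concern.** There are two linked problems.

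First, the factor list decides how the central program allocates patients, and it is the list an analysis should reflect. Two current parts of the protocol give different lists.

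Second, minimisation deliberately balances the arms on these factors. If they are prognostic, the true variability of the treatment contrast is lower than under simple randomisation. An unadjusted analysis still uses the simple-randomisation variance, so its standard error is somewhat too large. Section 9.0 judges the trial by whether a DFS difference lies within about 7 percentage points, at a planned power of only 80%. An interval wider than it need be therefore gives away power that the design has already paid for.

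**Working it through.** **1. The texts side by side**

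| Place | Centre | FIGO stage | Age at 70 |
|---|---|---|---|
| Synopsis, Study Design | yes | yes | no |
| Section 8.0 | yes | yes | yes |
| 10.2, primary logrank | no | no | no |
| 10.2, secondary regression | factors not listed | factors not listed | factors not listed |
| 10.2, exploratory models (open list) | not named | named | named (no cut-point) |

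**2. The plan's own sample size.** Section 9.0 gives 90% DFS at 4.5 years in the control arm, a margin of 7.2 points, 80% power, 95% confidence and 740 patients. Use two one-sided tests on the difference, each at 0.025, with the 20% type II error split over the two sides (z = 1.2816):

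n per arm = (1.96 + 1.2816)² × 2 × 0.9 × 0.1 / 0.072² = 10.51 × 0.18 / 0.005184 ≈ 365, so 730 in total, within 2% of 740.

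At 370 per arm: SE = √(0.18/370) = 0.02206; 0.072/0.02206 = 3.264; power = 2Φ(3.264 − 1.96) − 1 = 2Φ(1.304) − 1 ≈ 81%.

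**3. Size by variance explained.** If the balanced factors explain a share r of the outcome variance (0.9 × 0.1 = 0.09) and balance is complete, the true SE is √(1 − r) times the unadjusted one. The documents give no stage mix, no DFS by eligible stage and no centre variation, so these are assumptions:

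- Stage: 20% IA at 97% DFS and 80% IB1 at 88.25% (0.2 × 0.97 + 0.8 × 0.8825 = 0.90). Between-stage variance = 0.2 × 0.8 × 0.0875² = 0.001225; r = 0.001225/0.09 = 1.4%.
- Centre: SD of 3 to 5 points; r = 0.03²/0.09 = 1.0% to 0.05²/0.09 = 2.8%.

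| Assumption | r | √(1 − r) | SE too large by | z | Power |
|---|---|---|---|---|---|
| None prognostic | 0 | 1 | 0 | 3.264 | 81% |
| Stage only | 1.4% | 0.993 | 0.7% | 3.287 | 81.5% |
| Stage + centre SD 3 | 2.4% | 0.988 | 1.2% | 3.304 | 82% |
| Stage + centre SD 5 | 4.1% | 0.979 | 2.1% | 3.334 | 83% |

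**4. Size by simulation of the logrank itself.** The set-up was 740 patients, equal arms, exponential survival calibrated to 90% at 4.5 years, and 4.5 years of uniform accrual plus 4.5 years of follow-up (about 108 events). Assumed: 33 centres, stage shares 5/10/85%, 5% of patients over 70, and minimisation with a biased coin of 0.8. There were 20,000 runs per scenario, so the Monte Carlo error is about 1/√40,000 = 0.005 on the SD of Z and √(0.05 × 0.95/20,000) = 0.15 points on the rejection rate.

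| Scenario, unstratified logrank after minimisation | SD of Z (nominal 1) | Two-sided 5% rejection |
|---|---|---|
| No prognostic effect | 0.999 | 5.0% |
| Moderate: stage HR 3, age HR 1.5, centre SD 0.3 | 0.997 | 5.2% |
| Strong: stage HR 5, age HR 2, centre SD 0.6 | 0.960 | 4.2% |

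Simple randomisation gave 0.998 to 1.003 and 4.9% to 5.1%. The moderate result cannot be told from nominal (a separate run of 4,000 gave 0.979). The strong scenario is clearly below 1: 1/0.960 = 1.042, an SE about 4% too large. Carried to the proportion scale as a rough guide, 3.264/0.960 = 3.400 and power = 2Φ(1.440) − 1 ≈ 85%.

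**The case against.** Section 8.0 is the operative text and is clear in itself. The synopsis is a summary that drops one factor, and nothing shows that any patient was allocated by the wrong list. That is fair: the mismatch is an editorial correction, though one of the two places still has to change.

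An unadjusted primary analysis with adjusted secondary ones is a defensible, conservative choice, and the handling of strata and small centres is often left to the statistical analysis plan, which is not at hand. The covariate lists in 10.2 are also open-ended, so centre is unnamed rather than ruled out. This weakens the point but does not remove it. Section 10.2 itself places adjustment outside the primary comparison, so an analysis plan that made it primary would depart from the protocol.

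A logrank test gives no interval for a DFS difference, and the power figures above are for a difference of two proportions with complete follow-up. This also stands. The two calculations agree on direction and order of size, not on an exact figure.

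A reader might infer from section 2.3, which ranks stage first among prognostic factors, that stage must matter a great deal here. That passage concerns cervical carcinoma in general, whereas this trial admits only IA1 with lymphovascular invasion, IA2 and IB1. It does not establish strong prognostic separation within that range.

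**Conclusion.** Two facts need no assumption: the factor lists differ by age, and the primary logrank as written uses none of the allocation factors. The statistical consequence is conditional. If the factors are prognostic, the unadjusted analysis after minimisation is conservative, with a standard error about 0 to 4% too large. The cost is at most a few points of power: from 81% up to 82 to 83% under the variance assumptions, and about 85% in the strong simulated scenario. With moderate effects it is close to nothing. The size rests wholly on assumed stage mix, prognostic strength and centre variation.

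A reader might infer that the primary analysis is invalid, or that its standard error is certainly wrong. Neither follows. Type I error is not inflated (4.2% to 5.2% in the simulations, the upper value within Monte Carlo error of 5%), and 740 patients remain sufficient on the plan's own terms. This is a low-priority improvement.

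**What to change.** 1. **Synopsis.** List the section 8 factors: treating centre, FIGO stage, and age (≤70, >70). Check the list against the settings of the randomisation program.
2. **Primary test (10.2).** Make it a logrank test stratified by stage and age group as used in the minimisation, with a rule, fixed in advance, for merging sparse strata. If 5% of patients were over 70, that group would be about 37 patients (0.05 × 740).
3. **Primary estimate.** Report the 4.5-year DFS difference and its 95% interval adjusted for, or standardised over, the same factors on the absolute scale. One option is a weighted sum of stratum-specific Kaplan-Meier differences, with weights equal to each stratum's share of randomised patients. A hazard ratio from a Cox model alone would not do, because the 7.2-point margin is an absolute difference.
4. **Centre.** Include it only after pooling small centres, for example by region. With an assumed 33 centres and about 108 events, there would be roughly 3 events per centre.
5. **Sensitivity.** Keep the unadjusted logrank and the unadjusted difference.

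The cost is one protocol wording change and a short specification of the standardised estimator. No extra patients, visits or data are needed, because the factors are recorded at randomisation.
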